### **Aim 3: To explore the effects of resveratrol on skeletal muscle metabolism and function.**

*We hypothesize that resveratrol treatment will enhance mitochondrial metabolism and improve strength and contractility.* We will examine the effects of resveratrol on mitochondrial content, signaling molecules involved in mitochondrial biogenesis, DNA and protein oxidative damage, and mitochondrial respiration in human skeletal muscle. It is anticipated that mitochondrial ATP production and aerobic muscular function will improve in concert with enhanced insulin sensitivity.

This aim will make use of the **muscle biopsy specimens from Aim 1**. We will therefore examine the effects of resveratrol on muscle mitochondrial function and aerobic muscular function in **the same n=25 overweight, middle aged** (age 45-65) nondiabetic and diabetic subjects. Again, We will be utilizing the younger 21-44 year old population to assess whether resveratrol has the same beneficial effects in younger subjects.

Following administration of resveratrol (n=55) for 28 days, we will examine:

1. Muscle mitochondrial content
2. Muscle mitochondrial function
3. Muscle strength and mobility

**Muscle biopsies:** human skeletal muscle biopsies will be obtained as described above, and stored at -80 °C for analysis of the following:

- mitochondrial content
- signaling molecules involved in mitochondrial biogenesis
- DNA and protein oxidative damage, and
- mitochondrial respiration
- skeletal muscle mitochondrial function (citrate synthase and succinate dehydrogenase activity), content, and morphology by electron microscopy.

**Muscle strength and mobility tests:** will be conducted by our collaborators from the Department of Neurology and assess the following:

- **Mobility measures:** Quantitative gait studies will be conducted using a 28-foot (20 feet recording surface) computerized walkway with embedded pressure sensors (GAITRite, CIR systems). Subjects will walk on the mat at their „normal pace“ for two trials in a quiet well-lit room wearing comfortable footwear and without any attached monitoring devices. The walkway includes four unmarked feet at either end to account for initial acceleration and terminal deceleration. Based on footfalls recorded on the walkway, the software automatically computes various gait parameters as the mean of two trials. The GAITRite system is widely used in clinical and research settings, with excellent inter-rater and test-retest reliability (kappa >0.9) (88,89). Our collaborators in the Department of Neurology have experience using this system for the past 8 years in community based studies.
- **Walking while talking test (WWT):** Subjects are asked to walk the course for two trials while reciting alternate letters of the alphabet using protocols developed and validated in our subjects. Number of errors while reciting letters will also be recorded. Subjects are given practice trials as required. The order of the initial letter on WWT is also randomly varied between „A“ and „B“ to minimize practice effects. The WWT performance has been related to increased attention demands (90) and falls (91).
- **Chair rise:** Time taken to get up from a chair five times unassisted and without pausing is recorded (seconds). This test assesses lower extremity strength and balance, and is a component of the widely used Short Physical Performance Battery (92).
- **Unipedal Stance.** The unipedal stance measures ability to stand on one foot (maximum 30 sec), and is considered a sensitive measure of balance (93).
- **Stair climbing:** Difficulty with climbing up or down stairs is associated with functional limitations.
- **Muscle strength:** Tests of grip and leg strength is commonly used to assess power, and define frailty.

#### **Aim 4: To assess the effects of resveratrol on cognition.**

*We hypothesize that resveratrol will enhance cognitive function in middle-aged individuals.* In collaboration with the Department of Neurology we will therefore examine the effects of resveratrol on cognition in **the same n=25 overweight, middle aged** (age 45-65) nondiabetic and diabetic subjects. We will be utilizing the younger 21-44 year old population to assess whether resveratrol has the same beneficial effects in younger subjects.

Following administration of resveratrol (n=25) for 28 days, we will examine:

- **Executive control:** The Attention Network Test is a combination of the cued reaction time (RT) and the flanker task (94,95). The ANT provides estimates of three separate attention networks of alerting, orienting, and executive attention (95,96). Efficiency of the three attentional networks is assessed by measuring how response times are influenced by alerting cues, spatial cues, and flankers (i.e., congruent or incongruent conditions). The task is relatively short and simple so that reliable estimates of the three attention networks can be obtained within 35 minutes for various healthy and pathological populations.
- **Clinical neuropsychology battery:** provides comprehensive assessment of cognitive function (97,98,99). This battery consists of traditional, standardized measures of: a. intelligence, b. memory, c. language, d. executive function, e. visuospatial function and praxis, f. processing speed, and g. mental status. These tests were used in our previous research to demonstrate informative associations between cognitive and motor function (100,101,102).

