### **General Experimental Conditions:**

On the day of the first pancreatic clamp study the patients will receive a 28 days" supply of resveratrol capsules. The pilot study will be an open-labeled study. The study design requires that all 55 subjects participate in all of the proposed studies, as outlined below. Consequently, additional subjects will be recruited to compensate for those subjects who cannot complete all of the required studies.

Prior to each study, subjects will meet with study personnel to discuss dietary recommendations. Each subject will be instructed to follow a standardized diet plan for three days prior to each of the clamp studies (40% fat: 20% saturated, 10% polyunsaturated, 10% monounsaturated; 35% carbohydrate; 25% protein). Subjects will be asked to refrain from vigorous exercise for three days prior to each clamp study.

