### Schedule of proposed clinical studies:

**Day -1:** Subjects visit the Ferkauf School of Psychology at 8 am for motor and cognitive function tests. Subject with type 2 diabetes will present at 2 pm for cognitive and motor testing then be admitted to Weiler Hospital at 5 pm the night before the clamp study.

**Day 0:** Subjects admitted to GCRC at 8 am following a 10 hour fast,

- first stepped insulin clamp study
- fat and muscle biopsies

**Days 1-28:** Subjects receive oral resveratrol (last dose on day of final clamp study)

**Day 27:** Subjects visit the Ferkauf School of Psychology at 8 am for motor and cognitive function tests. Subject with type 2 diabetes will present at 2 pm for cognitive and motor testing then be admitted to Weiler Hospital at 5 pm the night before the study.

**Day 28:** Subjects admitted to GCRC at 8 am following a 10 hour fast

- second stepped insulin clamp study
- fat and muscle biopsies

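### As scheduled, with all subjects on open-label resveratrol, a rise in Aim 4 cognitive scores between day -1 and day 27 could not be separated from practice on the tests

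*Combined protocol and SAP*

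**What the plan says.** All references are to the combined protocol and SAP.

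- **Aim 4 hypothesis.** "We hypothesize that resveratrol will enhance cognitive function in middle-aged individuals". The tests are the Attention Network Test and a clinical neuropsychology battery covering seven domains, from intelligence and memory to processing speed and mental status.
- **Timing.** The schedule of proposed clinical studies has the same entry for day -1 and day 27: "Subjects visit the Ferkauf School of Psychology at 8 am for motor and cognitive function tests". Subjects with type 2 diabetes are tested in the afternoon of the same two days.
- **Design as scheduled.** General Experimental Conditions states "The pilot study will be an open-labeled study". The Aim 1 section gives all 55 subjects a 28-day course of resveratrol and compares each with his or her own day 0. The schedule contains no placebo arm or placebo period.
- **Practice control.** For the walking-while-talking test the Aim 3 section says "Subjects are given practice trials as required. The order of the initial letter on WWT is also randomly varied between" two letters, and gives the reason: "to minimize practice effects". This is the only place where practice effects are named.
- **Aim 4 tests.** The battery is described only by domain ("This battery consists of traditional, standardized measures of"), and the Attention Network Test by its scoring: "Efficiency of the three attentional networks is assessed by measuring how response times are influenced by alerting cues, spatial cues, and flankers". No alternate forms, practice session or practice-adjusted change score is stated for either.
- **Analysis.** Statistical Analysis describes paired t-tests and ANOVA for glucose uptake. For cognitive scores it offers only the general promise of descriptive statistics for all variables.

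**The concern.** People often score better the second time they take a cognitive test, because they know the task and may remember the items. The plan accepts this for one test and acts on it. The tests that carry Aim 4 have no stated protection, and they are repeated after 28 days in subjects who have all taken the drug in the interval.

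Practice and the hypothesised drug effect both push scores upward. With no untreated subjects retested on the same schedule, the data contain nothing that tells the two apart. A before-after comparison then answers whether scores rose on retest, while Aim 4 asks whether resveratrol raised them. What is at stake is the conclusion of one of four numbered aims. The principal endpoint, clamp glucose uptake, is not affected.

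The concern is strongest for memory, executive and speed tests. It is weaker for the attention-network scores, because these are contrasts between conditions and general speeding may partly cancel.

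**Working it through.** The plan gives no figure to reproduce: it states no practice gain, retest correlation, significance level or power for the cognitive scores. The calculation below only illustrates how large the problem could be.

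**Inputs from the documents**
- Retest interval: 27 − (−1) = 28 days (schedule).
- Sample size: n=25 in the Aim 4 section; n=55 in General Experimental Conditions, which has all subjects take part in all studies. Both are shown.

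**Assumptions**
- Inert drug, so the mean change is practice alone.
- Paired t-test, two-sided 5%.
- Retest correlation r = 0.7 or 0.8, with equal SD at both sessions.
- Practice gain d = 0.1, 0.2 or 0.3 baseline SD.

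**Formulas**
- SD of change, in baseline SD units: √(2(1 − r)). This is √0.6 = 0.775 at r = 0.7 and √0.4 = 0.632 at r = 0.8.
- Standardised change: dz = d / √(2(1 − r)).
- Noncentrality: dz × √n. The chance of a significant improvement is the upper-tail probability of the noncentral t with n − 1 degrees of freedom beyond the critical value (2.064 at n=25, 2.005 at n=55).

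**One case in full.** With d = 0.2 and r = 0.8, dz = 0.2/0.632 = 0.316. At n=25 the noncentrality is 0.316 × 5 = 1.58 and the probability is 33%. At n=55 it is 0.316 × 7.416 = 2.35 and the probability is 63%.

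**Chance of a significant improvement on one score, from practice alone**

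| Practice gain (SD) | n=25, r=0.7 | n=25, r=0.8 | n=55, r=0.7 | n=55, r=0.8 |
|---|---|---|---|---|
| 0 | 2.5% | 2.5% | 2.5% | 2.5% |
| 0.1 | 9% | 11.5% | 15% | 21% |
| 0.2 | 24% | 33% | 47% | 63% |
| 0.3 | 46% | 62% | 81% | 93% |

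At a gain of only 0.05 SD the figures are about 5–6% at n=25 and 7–8% at n=55.

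**Check on the cause.** With two concurrent randomized arms tested on the same schedule, mean practice gain cancels. In a simulation of 40,000 trials per setting (total N of 25 and 55, practice gain 0.3 and 0.5 SD of change), the two-sided false-positive rate was 0.049–0.050. The inflation therefore comes from the lack of a concurrent control.

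**The case against.** **The plan mentions placebo.** The Overview refers to clamps after both placebo and resveratrol, and Statistical Analysis to two groups randomized to resveratrol or placebo. If that text governed, practice would balance between arms and most of this point would fall away. But General Experimental Conditions, the Aim 1 section and the schedule contain no placebo, and the analysis text gives 45 days of treatment where the schedule gives 28. These sections contradict each other and must be reconciled. The point holds for the design as scheduled, and only for that.

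**This is the missing control arm under another name.** The cause is the same, but part of the remedy differs: form order, practice trials and the wording of the conclusion can change within the two existing sessions.

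**Alternate forms may already be in use.** The battery is listed by domain with references that could not be consulted here. The most that can be said is that the protocol does not state them. If they exist, a sentence settles that part.

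**The aim is not principal and the study is a pilot.** True, and it limits the weight of the point.

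A reader might also infer that the motor battery is compromised. The documents do not support that. Walking-while-talking has its own control, and nothing shows a practice gain for normal-pace gait or for strength. The gait text claims "with excellent inter-rater and test-retest reliability". Reliability does not rule out a mean shift, but neither is it evidence of one.

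**Conclusion.** The concern holds for the Aim 4 cognitive tests, on condition that the study is run single-arm as scheduled. A rise from day -1 to day 27 could not be separated from practice.

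Across retest correlations of 0.7 to 0.8, the illustrated chance of a significant improvement on one score with an inert drug runs from 9–11.5% (n=25) and 15–21% (n=55) at a 0.1 SD gain to 46–62% and 81–93% at 0.3 SD, against a nominal 2.5%. The gain, the correlation, the paired t-test and the 5% level are all assumed. The range shows sensitivity and is not a forecast for any particular test; the attention-network contrasts may sit lower.

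A reader might go further and infer that practice gain would be reported as cognitive benefit. The documents do not say so: they specify no test for cognitive scores and contain no Aim 4 conclusion. What they support is that the two explanations cannot be told apart. This is a cheap improvement to a non-principal aim.

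**What to change.** 1. Use parallel forms in counterbalanced order across day -1 and day 27 for each battery test that has them, and name those tests.
2. Give unscored practice before the Attention Network Test, at least before the scored run on day -1.
3. While the study stays single-arm, state that Aim 4 results will be reported as change on retest and not as an effect of resveratrol.
4. Reconcile the placebo and randomization wording in the Overview and Statistical Analysis with General Experimental Conditions, Aim 1 and the schedule.

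Steps 1 and 2 reduce practice gain but do not remove it, since task familiarity still favours the second session. Step 3 is what prevents misattribution.

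Cost: a few minutes per session, slightly more variance from differences between forms, and a weaker Aim 4 conclusion. No visit is added. A concurrent randomized control would deal with the cause but is a much larger change: for an assumed true difference of 0.5 SD of change, power would be about 24% at a total of 25 subjects and 46% at 55, and 80% would need 63 per arm.

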### Schedule of proposed clinical studies:

**Day -1:** Subjects visit the Ferkauf School of Psychology at 8 am for motor and cognitive function tests. Subject with type 2 diabetes will present at 2 pm for cognitive and motor testing then be admitted to Weiler Hospital at 5 pm the night before the clamp study.

**Day 0:** Subjects admitted to GCRC at 8 am following a 10 hour fast,

- first stepped insulin clamp study
- fat and muscle biopsies

**Days 1-28:** Subjects receive oral resveratrol (last dose on day of final clamp study)

**Day 27:** Subjects visit the Ferkauf School of Psychology at 8 am for motor and cognitive function tests. Subject with type 2 diabetes will present at 2 pm for cognitive and motor testing then be admitted to Weiler Hospital at 5 pm the night before the study.

**Day 28:** Subjects admitted to GCRC at 8 am following a 10 hour fast

- second stepped insulin clamp study
- fat and muscle biopsies

### STATISTICAL ANALYSIS

Data collected from each subject will be edited, entered, verified and entered into a FoxPro data base system in the GCRC. Data quality checking will be performed by computer programs designed to detect errors using accepted ranges, logic checks, and missing values. Outliers will be checked against the original record and correct values will be entered into a final data file. Data from FoxPro files will be transferred into SAS System Version 6.12 (SAS Institute, Cary, NC) for analysis. We shall utilize SAS for all data management and statistical analysis. Descriptive statistics of all the variables at different time points will be derived and reported.

For the specific aims of this study, repeated measurements of several parameters including glucose metabolism and gene expression will be measured in each subject, with the principal endpoint being the rate of whole-body glucose uptake during the final hour of the high insulin clamp. The null hypothesis is that glucose uptake will be equal in each pair of experiments (ie. prior to and following 45 days" treatment with resveratrol or placebo). To determine the changes in glucose uptake between the paired experimental protocols for each subject group, paired Student's t-tests will be performed. For *between-group* comparisons (ie. between the two subject groups randomized to resveratrol or placebo), the principal endpoint will be the difference in whole-body glucose uptake ( $\Delta$ GU) between the 2 experimental conditions (eg. Resveratrol vs. placebo), with null hypothesis that the response to the experimental intervention will be the same in all subject groups. To determine the changes in glucose uptake between the paired experimental protocols for each subject group, analysis of

variance (ANOVA) will be performed by using PROC GLM in the SAS statistical package. Within group effects will be derived from the analysis.

*All values will be presented as the mean +/- SE.*

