### **Aim 1: To study the effects of resveratrol on age-related insulin resistance**

*We hypothesize that treatment of overweight, middle aged or Type 2 diabetes subjects with resveratrol will result in improved insulin sensitivity, as demonstrated by increased insulin-stimulated glucose uptake and enhanced insulin-mediated suppression of glucose production.*

We will study the following subject group:

- **Overweight and either young or middle aged** (BMI 25-30 kg/m^2, age 21-65) nondiabetic subjects, n=40 diabetic subjects (BMI=25-35) n=15

Each subject will receive a 28 day course of **resveratrol** (n=55). RevGenetics will supply the resveratrol (500 mg capsules; 2 capsules bid) for our proposed studies. A certificate of analysis has been provided by the manufacturer.

A comprehensive study of whole-body insulin action will be undertaken with specially designed „stepped” euglycemic (~90 mg/dl) -hyperinsulinemic clamp studies, both before and after administration of resveratrol.

Thus, we will compare the following parameters under paired conditions in each subject, on day 0 and day 28 of resveratrol treatment:

- a. **hepatic insulin action:** this will be determined as the ability of low infusion rates of insulin (20 mU/m^2.min above basal requirements) to suppress glucose production during the “**low insulin phase**” of the clamp studies.
- b. **peripheral insulin action:** this will be determined as the ability of high infusion rates of insulin (80 mU/m^2.min above basal requirements) to stimulate glucose uptake during the “**high insulin phase**” of the clamp studies.

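### The statistical section plans a randomised resveratrol-versus-placebo comparison after 45 days, but the design gives every subject 28 days of open-label resveratrol, so that principal contrast has no data

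*Combined protocol and SAP*

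**What the plan says.** All references are to the combined protocol and SAP.

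**Statistical Analysis**, the only statistical section, names two principal analyses.

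- Within subject: paired t-tests, "with the principal endpoint being the rate of whole-body glucose uptake during the final hour of the high insulin clamp". The null hypothesis is equal uptake "prior to and following 45 days" of resveratrol or placebo.
- Between groups: the difference in glucose uptake (ΔGU), compared "between the two subject groups randomized to resveratrol or placebo", by analysis of variance in PROC GLM.

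**The design sections** describe one treated cohort.

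- General Experimental Conditions: "The pilot study will be an open-labeled study". Supply is fixed at the first clamp: "On the day of the first pancreatic clamp study the patients will receive a 28 days" supply of resveratrol. The design requires that "all 55 subjects participate in all of the proposed studies".
- Experimental Approach, Aim 1: "Each subject will receive a 28 day course of" resveratrol (n=55, made up of 40 nondiabetic and 15 diabetic subjects), with paired measurements "on day 0 and day 28 of resveratrol treatment".
- Aim 2 repeats n=55 and 28 days.
- Schedule of proposed clinical studies: first clamp on day 0, resveratrol on days 1-28, second clamp on day 28. It has no placebo period, allocation step or day-45 visit.

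**The Overview** gives a third version: paired clamps in the same subject, one after placebo and one after resveratrol.

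**The concern.** An analysis plan has to be executable on the data the design produces. Here one of the two analyses labelled principal needs a randomised placebo group that the design sections never create. The treatment duration in the null hypothesis also differs from the one in the schedule.

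The unavailable contrast is the one that matters for attribution. A concurrent placebo group would absorb anything that changes between two clamps four weeks apart for reasons other than the drug. Examples are familiarity with the procedure, regression to the mean, and diet or activity changes on joining a study. The before/after test absorbs none of these. A reader who sees the statistical section could take a before/after change as placebo-controlled evidence.

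The surviving endpoint has a loose end of its own. The Glucose Kinetics paragraph gives averaging windows that do not match the clamp timetable as written.

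**Working it through.** The documents give no alpha, power, effect size, SD or sample-size calculation, so there is no stated figure to reproduce. The check is a count, a comparison of sections and some labelled illustrations.

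**1. Placebo data available.** Aim 1 gives 40 + 15 = 55 subjects, all on resveratrol. Placebo subjects = 55 − 55 = 0. With every subject coded treatment = 1, the treatment column equals the intercept. The two-column design matrix has rank 1, so PROC GLM cannot estimate resveratrol versus placebo.

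**2. Does the Overview's within-subject design supply placebo data?** In the schedule the first clamp precedes any treatment and the second follows resveratrol. The Human Subjects Involvement paragraph allows two infusion studies per subject. Two infusions alone would fit a placebo/resveratrol pair; the schedule is what rules it out. Neither clamp follows placebo.

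**3. Duration.** Statistical Analysis: 45 days. General Experimental Conditions, Aims 1 and 2, and the schedule: 28 days. The difference is 45 − 28 = 17 days, with no clamp planned at day 45.

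**4. Averaging window of the surviving endpoint.** The clamp timetable sets basal t=0-120, low insulin t=120-240 and high insulin t=240-360. The final high-insulin hour is therefore t=300-360.

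| Glucose Kinetics window | Minutes in basal | in low | in high | in t=300-360 |
|---|---|---|---|---|
| t=60-120 (called low insulin) | 60 | 0 | 0 | 0 |
| t=180-240 (called hyperglycemic) | 0 | 60 | 0 | 0 |

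Adding 120 minutes to each gives t=180-240 and t=300-360, exactly the final hours of the low and high phases. The paragraph may be counting from the start of the low phase, but it does not say so. The hyperglycemic label also conflicts with a clamp held at about 90 mg/dl throughout.

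**5. Size, for illustration.** Assume two-sided alpha 0.05, 80% power and effects in SDs of the within-subject change, with equal SDs across groups. The detectable effect d solves P(T > t(0.975, df)) = 0.80, where T is noncentral t:

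- paired: df = n − 1, noncentrality d√n;
- two groups: df = n1 + n2 − 2, noncentrality d√(n1·n2/(n1+n2)).

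| Comparison | Detectable d |
|---|---|
| Paired, n=55 | 0.385 |
| Paired, n=40 | 0.454 |
| Paired, n=15 | 0.778 |
| Nondiabetic vs diabetic, 40 vs 15 | 0.864 |
| Hypothetical placebo split, 28 vs 27 | 0.770 |

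Splitting the same 55 subjects doubles the detectable difference (0.770 / 0.385 = 2.0). Keeping 0.385 in a two-arm comparison needs 106.9, about 107 per arm.

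**The case against.** The strongest reply is that the first-named principal analysis still works. A single-arm open-label pilot is a legitimate design, and the between-group wording might be read as nondiabetic versus diabetic. The first two points are right, and nothing here requires a placebo arm. The third fails on the text: the section itself defines its groups by randomisation to resveratrol or placebo. A nondiabetic/diabetic comparison is computable but is not a treatment comparison.

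On the averaging window, the endpoint is clear in words and the uniform 120-minute shift makes both windows fit. That suggests a different time origin and a wrong label more than a wrong endpoint. This largely stands. The zero overlap holds only on the literal clock, and the point is a clarification that does not carry the main conclusion.

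On the figures, 55 is not the only sample size given. Recruitment Monitoring sets a goal of 40 completers. Recruitment and Informed Consent plans at least 40 nondiabetic and 45 diabetic subjects. Aims 3 and 4 refer to 25. With 40 completers the paired figure is 0.454 and a 20/20 split detects 0.909; with 40 versus 45 the nondiabetic/diabetic comparison detects 0.616. So the illustrations move with the count. The contradiction does not: no section allocates any subject to placebo.

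Finally, the plan specifies paired tests for each subject group, so naming a single primary analysis goes beyond reconciling the text. That is fair, and the change should be made openly.

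**Conclusion.** The concern holds and must be fixed before analysis. The principal between-group contrast has data from 0 of 55 subjects on placebo and cannot be estimated, and the treatment duration is 45 days in one section and 28 in the others. No other section resolves either conflict.

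The paired test remains computable from the planned samples, but it estimates change from baseline only. If the Glucose Kinetics windows were applied on the clamp clock, that endpoint would be averaged over the wrong phase; if they start at the low phase, it would not.

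The contradiction needs no assumption. The detectable effects rest on the assumed alpha, power, equal SDs and stated sample sizes, and serve only to show scale.

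**What to change.** The sponsor should reconcile the Overview, General Experimental Conditions, Aim 1, the schedule and Statistical Analysis on the control condition, and on 45 versus 28 days of treatment. Which applies is for the sponsor to settle.

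**If the open-label single-arm design stands:**

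1. Remove the randomised placebo comparison from Statistical Analysis and the placebo wording from both that section and the Overview.
2. Make the paired t-test on within-subject change in whole-body glucose uptake, final hour of the high-insulin phase, the single primary analysis. State which subjects it includes, and what becomes of the per-group paired tests. Put Glucose Kinetics on the same clock as the clamp timetable (high phase t=240-360) and correct the period label.
3. Say which existing groups are meant by subject group: nondiabetic versus diabetic, or ages 21-44 versus 45-65. Label any comparison between them secondary and not a treatment comparison.
4. State that the trial estimates change from baseline and cannot by itself attribute that change to resveratrol.

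The cost is wording, mainly in the Overview, Glucose Kinetics and Statistical Analysis; causal language in Specific Aims and Rationale should be brought into line. The downsides are a weaker stated conclusion and an imprecise secondary comparison (0.864 SD for 40 versus 15, on the assumptions above).

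**If a placebo comparison is intended,** General Experimental Conditions, Aim 1 and the schedule must describe the placebo, the allocation and the visits. That is a redesign: splitting the same 55 raises the detectable difference to 0.770 SD, and keeping 0.385 SD takes about 107 per arm.
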